The Bridge device, currently FDA approved for opioid use disorder, acts as a peripheral nerve stimulator/modulator. Nerves potentially affected by the electrodes placed on and around the ear include the auriculotemporal branch of the Mandibular Nerve, the posterior auricular branch of the Facial Nerve, the Glossopharyngeal Nerve, and the auricular branch of the Vagus Nerve, as well as the peripheral occipital and greater auricular nerves. This stimulation is believed to provide analgesic effects through influence on various neurotransmitters, including serotonin, norepinephrine and GABA, and has resulted in 56-75% reduction of opioid requirements in major abdominal surgery (4).

The device has an integrated 3 volt battery, with an impedance range of 1 to 10 kilo-ohms. It provides symmetrical, biphasic stimulation at a frequency of 0.125 Hz. Its package notes that it is contraindicated for patients with pacemakers, those with hemophilia (since the electrodes involve a micro-needle puncture), and psoriasis involving the ear. We would broaden this to include any patient with active anticoagulation, or any dermatologic condition involving the skin of the ear where the device would be placed.

Study Hypothesis: Use of the Bridge device will reduce opioid requirements (after resolution of block) by more than 33% on postoperative days 1 through 5.

Primary Outcome: Cumulative Oral Opioid Use (expressed as Oral Morphine Equivalents) on Postoperative days 1 through 5.

Secondary Outcomes: NRS pain scores recorded every four hours on postoperative days 0 to 4,
Oral opioid use on Individual Postoperative days 5 through 7
NRS pain scores recorded every 8 hours on postoperative days 4 to 7
Adverse effects related to opioids (nausea, dizziness, vomiting, itching)
Local adverse effects on ear related to use of bridge device (pain, etc)

Setting: UPMC West Mifflin Ambulatory Surgery Center, West Mifflin, PA. Specifically with use in ambulatory rotator cuff repair patients.

Subjects: We plan to enroll 15 patients in this observational, "proof of concept" study, in order to evaluate whether a 33% reduction in opioid use is possible over postoperative days 1 through five (after resolution of block), as compared to historical controls.

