Procedures: Informed consent will be obtained, per IRB requirements. Standard anesthesia will be provided for rotator cuff repair for all patients. This includes single-shot bupivacaine interscalene nerve block with propofol sedation for the surgery itself, followed by application of the Bridge device in consented patients. Application of Bridge device occurs after surgery in recovery area. The ear is scrubbed with alcohol and electrodes placed in the required areas on or just in front of auricle. The device is then activated in the PACU. Patients will fill out a "pain diary" at home to record oral opioid use and pain scores as noted above, for first seven days after surgery. A study coordinator will call the patients on postoperative day 1, 3 and 7 to evaluate them. The device becomes inactive after 5 days and will be removed and discarded. At the end of 7 days, patients will fill out a Quality of Recovery survey, as well as a survey about the impact of the use of the device on their pain and recovery.

Endpoints: These include the primary and secondary outcomes noted above. At the end of five days, the device will be removed by the patient and discarded. Any patient who develops pain or skin irritation (or other adverse reaction) from the Bridge device will be advised to remove it and their participation will be stopped at that time.

Data Analysis: Descriptive statistics will be utilized, including comparison to historic controls. Mean pain values based on recorded NRS score for each postoperative day will be compared between groups. For the primary outcome, opioid ingestion over the entire interval of postoperative days 1 to 5 will be expressed as mean OME for each group, reported with 95% confidence interval. In pain scores, a difference of at least 1.7 on NRS scoring is considered to represent a meaningful clinical difference for shoulder surgery.

1. Abdallah FW Anesth Analg 2015;120:1114.
2. Hussain N. Anesthesiology 2021;134:147
3. [name]. J Complement Integr Med 2021 doi:10.1515/jcim-2021-0208

4. Ilfeld BM Reg Anesth Pain Med 2022;47:581

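### The 33% opioid target is worded in two ways, and the planned analysis gives no interval for the reduction, so one result could be called a success or a failure

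*Combined protocol and SAP*

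**What the plan says.** The Study Hypothesis reads "Use of the Bridge device will reduce opioid requirements (after resolution of block) by more than 33% on postoperative days 1 through 5". The Primary Outcome is "Cumulative Oral Opioid Use (expressed as Oral Morphine Equivalents) on Postoperative days 1 through 5".

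The Subjects paragraph then gives the reason for the sample size. It begins "We plan to enroll 15 patients in this observational", labels the study a proof of concept, and states the purpose as "in order to evaluate whether a 33% reduction in opioid use is possible over postoperative days 1 through five", "as compared to historical controls".

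Data Analysis opens with "Descriptive statistics will be utilized, including comparison to historic controls". For the primary outcome, opioid intake over days 1 to 5 "will be expressed as mean OME for each group, reported with 95% confidence interval". It plans no interval for the difference or ratio between groups, no test, and no rule for judging 33%. The documents give no SD for cumulative OME, no control mean and no number of controls.

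**The concern.** The two sentences ask different things of the data. To support a reduction of more than 33%, the data should rule out reductions of 33% or less. To show that a 33% reduction is possible, they need only fail to rule it out. A third, equally natural reading is that the observed reduction should exceed 33%. The plan does not choose among them.

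The planned output does not settle it either. The hypothesis concerns a ratio of two means, and an interval around each mean is not an interval for that ratio. A reader of the results could not tell directly how precisely the reduction was estimated.

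The 33% figure is the only threshold the plan sets for opioid use (the 1.7-point figure in Data Analysis concerns pain scores). If its reading is chosen after the data are seen, the conclusion on the primary outcome has no defined error rate.

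**Working it through.** **Inputs from the documents:** 15 device patients; 33% threshold, that is, a Bridge/control ratio of 0.67; 95% intervals.

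**Assumed, because not given:** CV of days 1–5 OME between 0.4 and 1.2, the same in each group; control mean treated as known unless stated.

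**The plan's own figure.** The 15 cannot be reproduced, as no inputs are stated. Working backwards, a one-sample comparison with 80% power to detect a 33% reduction against no reduction gives 15 only if the CV is about 0.45 (two-sided) or 0.50 (one-sided). That would be a test against zero reduction, not against 33%.

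**Precision with 15 patients.** t(14, 0.975) = 2.145, so the half-width of the 95% interval, as a fraction of the Bridge mean, is 2.145 × CV/√15 = 0.554 × CV.

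**An observed 40% reduction (ratio 0.60).** The interval for the ratio is 0.60 × (1 ± 0.554 × CV). At CV 0.8 the half-width is 0.60 × 0.443 = 0.266, so the ratio runs from 0.334 to 0.866, a reduction of about 13% to 67%. The last column is the observed reduction at which the upper limit reaches 0.67, from 1 − 0.67/(1 + 0.554 × CV).

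| CV | 95% interval for an observed 40% reduction | Observed reduction needed to establish more than 33% |
|---|---|---|
| 0.4 | 27% to 53% | 45% |
| 0.6 | 20% to 60% | 50% |
| 0.8 | 13% to 67% | 54% |
| 1.0 | 7% to 73% | 57% |
| 1.2 | 0% to 80% | 60% |

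In every row a 40% result passes the point-estimate reading, passes the possible reading and fails the more-than-33% reading. To exclude 33% it would need a CV below (0.67/0.60 − 1)/0.554 = 0.21.

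**Uncertainty in the controls widens this.** With 15 controls and CV 0.8, the standard error of the log ratio is 0.8 × √(1/15 + 1/15) = 0.292. With t(28) = 2.048, the ratio runs from 0.60 × exp(−0.598) = 0.33 to 0.60 × exp(0.598) = 1.09, that is, from a 67% reduction to a 9% increase.

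**How often each reading would be met.** These are simulations with gamma-distributed OME, 15 patients, a known control mean and a 95% interval on the log-ratio scale.

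- Device with no effect, 33% not excluded: about 6% to 34% of studies at CV 0.4–0.6, and 57% to 78% at CV 0.8–1.2.
- Device with no effect, observed reduction above 33%: about 4% at CV 0.8 and 9% at CV 1.0. With 15 controls these become 9% and 14%.
- True reduction 33%, observed reduction above 33%: about half of studies.
- More than 33% established: 21% to 45% of studies at a true 50% reduction, and 32% to 74% at a true 56% reduction (CV 0.6–1.2).

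**The case against.** The strongest reply is that the study calls itself an observational proof of concept with descriptive analysis, so no formal test is promised. On this view the two sentences express one aim: a hypothesis, and a small study to see whether it looks achievable. Much of this stands. It removes any demand for a powered test or a significance requirement. It does not remove the need to say how the one opioid threshold will be read, since a proof of concept informs a decision to proceed, and here that decision is tied to a number.

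A reader might go further and infer that the plan sets two opposing tests, one almost unreachable with 15 patients and the other usually passed by an inert device. The documents do not support that, for three reasons.

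- The plan sets no test. The strict and lenient criteria are constructions from the two wordings, and the point-estimate reading fits neither description.
- Establishing more than 33% is hard mainly if the true reduction is near 33–40%. The background cites reductions of 56–75%, though in major abdominal surgery, and at a true 56% the strict criterion would be met in 32% to 74% of studies under the assumptions above.
- An inert device usually leaves 33% unexcluded only at the higher CVs. At CV 0.4–0.6 it does so in about a third of studies or fewer with a known control mean. The CV is assumed.

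Nor do the documents show how many controls are available, so a demand for a particular number would have no basis in them.

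**Conclusion.** The concern holds as a gap in the stated criterion and the planned estimate. The 33% target appears in two non-equivalent wordings, no rule chooses between them, and the primary analysis provides no interval for the quantity the hypothesis is about.

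That a 40% result would be ambiguous holds across the whole assumed CV range of 0.4–1.2, even with a perfectly known control mean. The width of the ambiguous zone and the pass rates do depend on the CV, the distribution and the number of controls, none of which is stated, so they are illustrations and not properties of this trial. This is worth correcting before outcome data are seen. It does not invalidate a descriptive pilot.

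**What to change.** 1. **Data Analysis.** Make the primary result the ratio of mean days 1–5 OME (Bridge over historical control) with a 95% interval that allows for uncertainty in the control mean, and name the interval method in advance. The separate group means can stay as supporting description.
2. **Decision wording.** For example: *A reduction of more than 33% will be claimed only if the upper 95% limit of the OME ratio is below 0.67. Otherwise the observed reduction and its interval will be reported as an estimate, and the hypothesis will be described as unconfirmed.*
3. **Subjects.** Say that the 15 patients are enrolled to estimate the reduction relative to historical controls, and drop possibility as a criterion.
4. **Do not write a fixed required reduction, such as 50–60%, into the protocol.** That range comes from an assumed SD and a known control mean. On a log-ratio interval with 60 controls it would be about 53–68% for CV 0.6–1.2.

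**Cost:** a change of wording and one further calculation, with no extra patients. The analysis needs the control group's mean, SD and number of patients. The downside is that an observed reduction modestly above 33% could no longer be presented as confirming the hypothesis.

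### The primary opioid total comes from a home diary kept by unblinded patients with no stated dose reconciliation; if control capture was more complete, omitted doses push the result toward the 33% target

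*Combined protocol and SAP*

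**What the plan says.** All references are to the combined protocol and SAP.

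- **Primary Outcome:** "Cumulative Oral Opioid Use (expressed as Oral Morphine Equivalents) on Postoperative days 1 through 5".
- **Study Hypothesis:** "Use of the Bridge device will reduce opioid requirements (after resolution of block) by more than 33% on postoperative days 1 through 5". The Subjects paragraph says that the 15 enrolled patients will be compared with historical controls. It does not say how opioid use was measured in those controls.
- **Procedures, data source:** "Patients will fill out a 'pain diary' at home to record oral opioid use and pain scores as noted above, for first seven days after" the operation. No other source of opioid data is named.
- **Procedures, staff contact:** "A study coordinator will call the patients on postoperative day 1, 3 and 7 to evaluate them". The content of these calls is not described further.
- **Procedures and Endpoints, awareness of the device:** anaesthesia and block are "followed by application of the Bridge device in consented patients", and "At the end of five days, the device will be removed by the patient and discarded". No sham or blinding is described.
- **Data Analysis:** "opioid ingestion over the entire interval of postoperative days 1 to 5 will be expressed as mean OME for each group", with a 95% confidence interval. There is no rule for missing entries or missing days.

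**The concern.** The primary value is a sum of doses that each patient enters at home. In a sum, a dose that was taken but not written down adds nothing. If the rest of the diary is complete, nothing marks the omission, so no missing-data rule could recover it. Only a second measure of intake could show it, and the plan states none.

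Patients also know they are wearing the device and are surveyed about its effect on their pain and recovery, so knowledge of the device could influence what they report.

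At stake is the study's single claim, a percentage reduction against a threshold. With one device group, no concurrent control and a descriptive analysis, under-recording that was heavier in the Bridge group than in the controls would look the same as a device effect. It could not be repaired afterwards, because tablets not counted during the study cannot be counted later.

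**Working it through.** The plan gives no control mean, no expected diary completeness and no capture rate for the controls, so there is no figure of its own to reproduce. The check asks how much unrecorded use would matter against the plan's 33% threshold.

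**Inputs**
- Threshold: 33% reduction (Study Hypothesis).
- r: true reduction in OME. Assumed, 0% to 30%.
- u_B: share of OME not recorded in the Bridge group. Assumed.
- u_H: share of OME not recorded in the historical controls. Assumed.

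**Formula**

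Apparent reduction = 1 − (1 − r)(1 − u_B)/(1 − u_H)

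**1. Controls fully captured (u_H = 0), true reduction 20%**
- u_B = 10%: 1 − 0.80 × 0.90 = 28%
- u_B = 20%: 1 − 0.80 × 0.80 = 36%
- u_B = 25%: 1 − 0.80 × 0.75 = 40%

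**2. Unrecorded share that brings the apparent reduction to 33%, controls fully captured**

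u_B = 1 − 0.67/(1 − r)

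| True reduction | Calculation | Unrecorded share needed |
|---|---|---|
| 0% | 1 − 0.67/1.00 | 33% |
| 10% | 1 − 0.67/0.90 | about 26% |
| 20% | 1 − 0.67/0.80 | about 16% |
| 30% | 1 − 0.67/0.70 | about 4% |

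**3. Controls also under-recorded**
- Equal shares (u_B = u_H = 20%), true reduction 0%: 1 − 1.00 × 0.80/0.80 = 0%. The error cancels.
- Bridge 10%, controls 20%, true reduction 0%: 1 − 1.00 × 0.90/0.80 = −12.5%. The device appears to increase use by 12.5%.
- Controls 10%, true reduction 20%: reaching 33% needs u_B = 1 − 0.67 × 0.90/0.80, about 25%, against about 16% with complete control data.

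The sign of the bias therefore depends on whether u_B is larger or smaller than u_H. The plan gives no information on u_H.

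**The case against.** The strongest reply is that the direction of bias is not established. If the control data also came from patient diaries, similar lapses could cancel; if control capture was poorer, the comparison would be biased against the device. This stands, and any statement of direction has to be conditional.

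Other stronger readings are tempting but go beyond the documents:

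- **Every missing entry is scored as zero.** No missing-entry rule is stated. Wholly blank days could be excluded or imputed. The argument holds only for a dose left out of an otherwise completed diary.
- **The calls do not check intake.** The plan is silent on this. A dose review may be intended, but it is not stated.
- **Patients know that the aim is to reduce opioid use.** Awareness of the device is clear. What patients are told about the aim cannot be seen in the available text.
- **Lapses are likely because the diary is demanding.** Frequent pain ratings could as easily prompt a patient to record a dose.

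It is also fair to say that the assumed shares have no source in the documents, and that with no true effect a third of all OME would have to go unrecorded to reach the threshold. A 15-patient proof-of-concept study can accept some measurement error. None of this removes the core gap: an omission in a completed diary is invisible, and the plan states no means of finding it.

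**Conclusion.** The concern holds in conditional form. The primary outcome depends on an unblinded patient's diary with no stated reconciliation, and undetected omissions lower the Bridge mean. They bias the result toward the 33% target only if opioid capture was more complete in the historical controls than in the Bridge group. Assuming complete control data, about 16% of OME unrecorded makes a true 20% reduction read as 33%, and about 4% is enough when the true reduction is 30%.

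A reader might infer that the diary necessarily favours the hypothesis. The documents do not support that, because the control capture method is not given.

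A reader might also infer that a tablet count should simply replace the diary as the primary measure. That does not follow either. If the controls were measured by diary, a count in the Bridge group alone would create a new mismatch between the groups.

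**What to change.** 1. State how opioid use was captured in the historical controls, and match the primary measure to it. Keep the diary total as primary unless the controls were measured by dispensing or tablet count.
2. Have patients write in the diary the number of tablets remaining of each opioid product, and any refill, at the start of POD 1 and the end of POD 5, or when participation stops if that is earlier.
3. Have the coordinator ask for the count at the existing POD 1, 3 and 7 calls and reconcile it with the diary. The POD 7 call should also confirm the count written down at the end of POD 5.
4. Give the diary a separate mark for no opioid taken, so that it differs from a blank.
5. Report the diary/count discrepancy for each patient, and a count-based OME as a sensitivity analysis: for each product, (starting count + refills − ending count) × OME per tablet, summed over products.

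The cost is a few diary lines and one question in calls already scheduled, with no new visit. The count is still reported by the same unblinded patient, so it helps more with forgetting than with reporting bias, and lost or shared tablets would count as taken. That is a further reason to use it as a sensitivity analysis unless the controls were measured in the same way.

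### The hypothesis credits the Bridge device with a reduction of more than 33% in opioid use, but an open, single-arm comparison with undescribed historical controls cannot attribute a difference to the device alone

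*Combined protocol and SAP*

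**What the plan says.** The Study Hypothesis reads: "Use of the Bridge device will reduce opioid requirements (after resolution of block) by more than 33% on postoperative days 1 through 5". The Subjects section sets the scale and label of the study, "We plan to enroll 15 patients in this observational, 'proof of concept' study", and asks whether a reduction of 33% is possible, "as compared to historical controls".

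Under Procedures, standard anaesthesia with a single-shot block is "followed by application of the Bridge device in consented patients". The device is placed and switched on in recovery. The patient wears it home, removes it after five days, and at day 7 completes a survey about its impact. No sham, masking, randomisation or concurrent group without the device is described.

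Follow-up of device patients has two parts:
- **Diary:** "Patients will fill out a 'pain diary' at home to record oral opioid use and pain scores as noted above". The Secondary Outcomes set the pain-score schedule: "NRS pain scores recorded every four hours on postoperative days 0 to 4" and "NRS pain scores recorded every 8 hours on postoperative days 4 to 7".
- **Calls:** "A study coordinator will call the patients on postoperative day 1, 3 and 7 to evaluate them". Nothing more is said about their content.

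The Data Analysis section plans descriptive statistics, with mean oral morphine equivalents (OME) for each group and a 95% confidence interval. It states no adjustment or matching. On the historical controls, the documents give no source, period, number, diary, contact or method of measuring opioid use.

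**The concern.** The hypothesis is a causal statement about the device, while the planned contrast compares two packages of care. One is the device worn knowingly, with a week of self-recording and three coordinator calls. The other is whatever the historical patients received.

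The primary outcome makes this matter. Opioid use at home is something the patient does, and expectation of benefit or contact with a coordinator can change how many tablets are actually taken. This is separate from the question of whether doses are recorded completely: a perfect diary would still capture a real reduction that the device did not cause.

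At stake is the conclusion the pilot permits. If a reduction above 33% is observed and read as the hypothesis is worded, the device is credited with an effect that the design cannot isolate. The label observational adds to the confusion, because the protocol itself applies the device.

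**Working it through.** **Step 1. Does the plan give a figure to reproduce?** The only design figures are 15 patients and 33%. No control mean, standard deviation, control number, alpha or power is given, so the 15 cannot be derived. The point does not depend on it.

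**Step 2. How much study contact do device patients have?**
- Calls are on POD 1, 3 and 7, and the primary window is POD 1 to 5. Two of the three (POD 1 and 3) fall inside it.
- Pain scores, counting full days: six a day at four-hourly intervals and three a day at eight-hourly intervals. POD 4 appears in both schedules. If it is eight-hourly, the count is 6 × 4 + 3 × 4 = 36. If it is four-hourly, it is 6 × 5 + 3 × 3 = 39.

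**Step 3. What part of an observed 33% reduction would belong to the device?** Let b be the proportional reduction from everything other than the device, and let the effects multiply. Then (1 − b)(1 − d) = 0.67, so d = 1 − 0.67/(1 − b). The values of b are assumed; the documents give none.

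| Assumed b | d, the device's part |
|---|---|
| 0% | 33.0% |
| 10% | 25.6% |
| 20% | 16.2% |
| 30% | 4.3% |
| 33% | 0% |

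All five rows produce the same two group means, so the planned analysis cannot tell them apart. A larger sample would narrow the interval around the combined effect but would not separate its components.

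**Step 4. How often would a device with no effect show more than 33%?** Inputs: 15 device patients (Subjects section); 60 controls, gamma-distributed OME, the coefficient of variation (CV) and the bias b are all assumptions. Each simulated trial draws the two group means, multiplies the device mean by (1 − b), and counts whether 1 − (device mean)/(control mean) exceeds 0.33, over 400,000 draws.

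| CV | b = 0 | b = 5% | b = 15% | b = 25% |
|---|---|---|---|---|
| 0.5 | 0.4% | 1.1% | 5.7% | 22.8% |
| 0.8 | 5.3% | 8.0% | 17.0% | 33.2% |
| 1.0 | 10.2% | 13.5% | 22.9% | 37.2% |

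With 15 controls instead of 60, the ranges over the same CVs are 1.5-14.0% at b = 0, 9.7-26.0% at b = 15% and 26.8-38.0% at b = 25%. The direction does not depend on the assumed number of controls. The size depends heavily on the CV and on b.

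**The case against.** The strongest reply is that the plan already limits itself. It describes a proof-of-concept study of 15 patients, asks what is possible, and plans only descriptive statistics, with no test, success rule or efficacy claim. The absence of a sham is normal at this stage. That is fair, and it is why a restatement is enough and a new design is not needed. But the formal hypothesis still credits the device, and nothing in the Data Analysis section says how a favourable result may be interpreted.

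Four stronger readings are tempting, and the documents support none of them:
- **The controls had no diary or calls.** The plan is silent. They could come from an earlier study with similar follow-up or from chart review. The silence means comparability cannot be judged; it does not show a difference.
- **The result will be reported as an effect of stimulation.** No such statement appears. The hypothesis speaks of use of the device, and stimulation appears only as the believed mechanism.
- **Patients are prompted for pain scores, or coached to use fewer opioids.** The text describes scheduled self-recording and calls for evaluation. It mentions no reminders and gives no call content.
- **The simulation measures this trial's error rate.** Every input except the 15 is assumed. The probability is small where bias or CV is low: 5.7% at a CV of 0.5 with a 15% bias. Nor does the plan commit to a point estimate above 33% as its criterion; it commits to group means with confidence intervals.

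**Conclusion.** The point holds as a mismatch between the hypothesis and the design. A single-arm, open-label study against historical controls of undescribed follow-up estimates the combined result of device, expectation, study contact and differences from past care. A conclusion drawn in the words of the hypothesis would not be supported.

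The size of the non-device part is unknown from the documents. The illustration shows only that an assumed non-device reduction of 15-25% would make an observed reduction above 33% clearly more likely with an inert device: about 6-37%, against 0.4-10% with no bias, for CVs of 0.5 to 1.0 and 15 against 60. The attribution problem itself rests on none of these assumptions. It follows from the design as described.

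The pilot can proceed. The hypothesis and permitted conclusion should be restated first. The design label is a smaller matter of terminology.

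**What to change.** 1. **Hypothesis and permitted conclusion.** Restate as: cumulative OME on POD 1 to 5 in patients given the Bridge device with study follow-up, compared descriptively with historical controls. Add that the result will inform whether a controlled trial is warranted and will not be presented as an estimate of the device's own effect.
2. **Design label.** Replace the word observational with: single-arm, open-label interventional pilot.
3. **Calls.** Conduct the POD 1, 3 and 7 calls from a fixed, neutral script that does not mention the opioid-reduction target.
4. **Controls.** State whether the historical controls had comparable diary and call contact, and if this is not known, say so.

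The cost is protocol wording, a short call script and a description of the control data. No extra patients or staff are needed. The downside is a more modest claim. These changes make the conclusion match the design; they do not isolate the device effect, which would need concurrent controls, ideally sham, with the same diary and calls.

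### No pain score is scheduled before surgery, so the daily NRS comparison with historical controls is unadjusted for pre-operative shoulder pain; Quality of Recovery is also not measured while the device is active

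*Combined protocol and SAP*

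**What the plan says.** **Pain.** The Secondary Outcomes section has two pain schedules: "NRS pain scores recorded every four hours on postoperative days 0 to 4" and "NRS pain scores recorded every 8 hours on postoperative days 4 to 7". Under Procedures the scores go into a diary that patients keep at home after surgery. The same section puts the anaesthetic and device steps before that: "This includes single-shot bupivacaine interscalene nerve block with propofol sedation for the surgery itself, followed by application of the Bridge device", and then "The device is then activated in the PACU". No pain score is listed at consent or before the block.

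**Comparison.** Under Subjects, the 15 patients are to be set against historical controls in an observational study. The Data Analysis section is descriptive and says "Mean pain values based on recorded NRS score for each postoperative day will be compared between groups". It names no baseline value and no covariate, and takes 1.7 NRS points as the smallest difference that matters clinically.

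**Recovery.** Procedures says "At the end of 7 days, patients will fill out a Quality of Recovery survey", and of the device, "The device becomes inactive after 5 days and will be removed and discarded". The version of the survey and its recall period are not given. A second day 7 survey asks patients to judge the device's effect on their pain and recovery. Coordinator calls are planned on postoperative days 1, 3 and 7. Quality of Recovery is not among the listed primary or secondary outcomes.

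**The concern.** Nothing in a comparison with historical controls balances the groups on how painful the shoulder was before the operation. If pre-operative pain predicts post-operative pain, a difference between the groups at the start carries into every daily mean and looks like a device effect, or hides one. The earliest diary score cannot serve as a baseline. It is taken at home on the day of surgery, after the block, the operation and device activation. A treated patient's pre-operative score also cannot be collected validly once the block and surgery have taken place, so the decision has to be made before enrolment.

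The recovery survey raises a smaller, separate question. Its only administration falls after the device has stopped working, so one score cannot separate recovery on the device from any change after removal.

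**Working it through.** The plan gives no figure for this point that could be reproduced: there is no SD, no number of controls and no baseline pain value. The check has three parts.

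**1. Is there any pre-operative score?** In time order:

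| Step | Pain score scheduled? | Recovery form scheduled? |
|---|---|---|
| Consent, before block | No | No |
| Block, surgery, device activated in PACU | No | No |
| At home, days 0 to 4 | NRS every 4 hours | No |
| At home, days 4 to 7 | NRS every 8 hours | No |
| Device inactive after 5 days | – | No |
| End of day 7 | (within diary) | Yes, once |

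Every pain score is post-operative. For the recovery form, the gap is 7 − 5 = 2 days, and 0 of 1 administrations fall in the device period.

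**2. How large could the pain bias be?** For an unadjusted difference in means,

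bias = slope of post-operative on pre-operative NRS × pre-operative difference between groups.

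Both inputs are assumptions, because the documents give neither. The yardstick of 1.7 comes from Data Analysis.

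| Slope (assumed) | Baseline difference (assumed) | Bias | Share of 1.7 |
|---|---|---|---|
| 0.3 | 1 | 0.3 | 18% |
| 0.3 | 2 | 0.6 | 35% |
| 0.5 | 1 | 0.5 | 29% |
| 0.5 | 2 | 1.0 | 59% |

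A deliberately wide range, with slope 0.2 to 0.7 and difference 1 to 3 points, gives 0.2 × 1 = 0.2 to 0.7 × 3 = 2.1 points (12% to 124% of 1.7). Only that most extreme corner exceeds the threshold; the next largest values are 0.5 × 3 = 1.5 and 0.7 × 2 = 1.4. At slope 0.5 the groups would have to differ by 1.7 / 0.5 = 3.4 points before surgery for the bias alone to reach 1.7.

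**3. What does a bias of that size do to the reading?** Over the main range it cannot produce a 1.7-point difference from nothing, but it can move a real difference across the line. A true benefit of 0.7 would appear as 0.7 + 1.0 = 1.7, and a true benefit of 1.7 could appear as 1.7 − 1.0 = 0.7.

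**The case against.** Several counter-arguments have force.

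- **Adjustment depends on the controls.** Scoring the 15 treated patients does not by itself permit any correction, because the controls need the same measure and the documents do not describe their data. This stands, and it makes the adjusted analysis conditional. If the charts hold a pre-operative score for controls, they may also hold it for the treated patients. The plan does not say so, and a scheduled question is safer than relying on it.
- **Pain is secondary and the study is small and descriptive.** The primary outcome is opioid use on postoperative days 1 to 5, which this point does not address. Baseline pain is one of many ways in which undescribed controls may differ, and adjusting for it would not repair that comparison. This also stands, and it keeps the point minor.
- **The size is assumed.** Correct: over the main range the bias stays under 1.7 points.
- **On-device and off-device experience is already tracked.** The diary records pain and opioid use during and after the device period, and two of the three calls fall within it. This answers most of the worry about the timing of the recovery survey.

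A reader might infer two stronger things. One is that no recovery score reflects the treated period. The documents do not support this: the recall period is unstated, so a day 7 form could look back over the device days, and the second day 7 survey asks about the device's effect in retrospect. What can be said is that no recovery form is completed while the device is active. The other is that pain differences can never be corrected for pre-operative pain. The documents show only that no such correction is planned and no such score is scheduled; they do not say what the charts contain.

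**Conclusion.** The point holds in a limited form, as a low-cost improvement rather than a serious defect. No pre-operative NRS is scheduled, and the daily pain comparison with non-randomised controls is therefore unadjusted for it. With an assumed 1 to 2 point baseline difference and a slope of 0.3 to 0.5, the bias is 0.3 to 1.0 NRS points, or 18% to 59% of the plan's threshold and not enough alone to reach it. Its direction is unknown. This affects a listed secondary outcome; nothing here bears on the primary outcome.

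The recovery-survey point is optional. Quality of Recovery is not a listed outcome, no analysis is planned for it and no control data are described, so better timing would inform on change within the treated group and nothing more.

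**What to change.** **Main change.**
1. Record one NRS at the consent or pre-operative contact, before the block.
2. Abstract pre-operative NRS for the controls from the chart, and state how many have it.
3. Report baseline NRS for both groups.
4. Add to Data Analysis a baseline-adjusted daily pain difference, shown beside the unadjusted one and restricted to controls with a value.

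The cost is one question per treated patient and one chart field per control. The downside is that fewer controls may be usable in the adjusted comparison, so the unadjusted difference should also be shown in that same subset. If no control has the value, the treated-group baseline is descriptive only and the report should say that adjustment was not possible.

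**Optional.** Name the Quality of Recovery version and its recall period. Give the form also at the existing day 3 call, and keep day 7 as the off-device follow-up. The cost is one short form at a contact already planned; the result should be labelled as within-group.
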